## Protocol summary

Title of the Study	Phase IIIb randomized trial comparing irradiation plus long term adjuvant androgen deprivation with GnRH antagonist versus GnRH agonist plus flare protection in patients with very high risk localized or locally advanced prostate cancer. A joint study of the EORTC ROG and EORTC GUCG.
Objective(s)	
The primary objective of the trial is to assess if GnRH antagonists in combination with external beam radiation therapy improve progression free survival (progression that can be biological, clinical, or death) compared to GnRH agonists in combination with external beam radiation therapy.
 
Secondary objectives include:
 
 
◆ documentation of effect of GnRH antagonists on clinically significant cardiovascular events in the subgroup of patients at high risk of such events at baseline;
 
◆ documentation of side effects and quality of life, I-PSS and urinary tract infections;
 
◆ assessment of relative treatment effect on secondary efficacy endpoints (clinical progression, time to next line of systemic therapy, time on therapy, overall and cancer specific survival) and on PSA at 6 months after end of RT.
 

Methodology	Phase IIIb randomized stratified open-label comparative 2-arm superiority study with a pre-set non-inferiority boundary.

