
Exclusion
	
agonist or GnRH antagonist use, because these drugs may prolong the QT-interval.
 
 
◆ WHO Performance status 0-1 (see Appendix C)
 
◆ Age <math>\geq 18</math> and <math>\leq 80</math> years
 
◆ Participants who have partners of childbearing potential must use adequate birth control measures, as defined by the investigator, during the study treatment period and for at least 3 months after last dose of study treatment. A highly effective method of birth control is defined as those which result in low failure rate (i.e. less than 1% per year) when used consistently and correctly
 
◆ Before patient registration/randomization, written informed consent must be given according to ICH/GCP, and national/local regulations.
 
 
Exclusion criteria
 
 
◆ Previous use of androgen deprivation therapy (ADT), antiandrogens. 5-alpha reductase inhibitors are allowed if interrupted for more than 6 months prior to entering the study
 
◆ History of severe untreated asthma, anaphylactic reactions or severe urticaria and/or angiodema.
 
◆ Hypersensitivity towards the investigational drug
 
◆ The following biological parameters :AST, ALT, total bilirubin, prothrombin time, serum albumin above upper level of normal range No severe hepatic impairment (Child Pugh C)
 
◆ History of gastro-intestinal disorders (medical disorder or extensive surgery) that may interfere with the absorption of the protocol treatment.
 
◆ History of pituitary or adrenal dysfunction
 
◆ Uncontrolled diabetes mellitus
 
◆ History of ulcerative colitis, Crohn's Disease, ataxia, telangiectasia, systemic lupus erythematosus, or Fanconi anemia.
 
◆ Clinically significant heart disease as evidence myocardial infarction, or arterial thrombotic events in the past 6 months, severe or unstable angina, or New York Heart Association (NYHA) class III or IV heart disease or cardiac ejection fraction measurement of <math>< 50\%</math> at baseline
 
◆ Coronary revascularization (PCI or multivessel CABG), carotid artery or iliofemoral artery revascularization (percutaneous or surgical procedure) within the last 30 days prior to entering the trial
 
◆ Certain risk factors for abnormal heart rhythms/QT prolongation: torsade de pointes ventricular arrhythmias (e.g, heart failure, hypokalemia, or a family history of a long QT syndrome), a QT or corrected QT (QTc) interval <math>>450</math> ms at baseline, or intake of medications that prolong the QT/QTc interval
 
◆ Uncontrolled hypertension (systolic BP <math>\geq 160</math> mmHg or diastolic BP <math>\geq 95</math> mmHg); patients with a history of hypertension are allowed provided
 

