
Criteria for evaluation
 
Efficacy
 
Safety
	
The primary endpoint is progression-free survival defined as the time in days from randomization to death, clinical or biochemical progression, whichever comes first.
 
Where
 
 
◆ PSA progression based on Phoenix definition, i.e. a rise by 2 ng/mL or more above the nadir PSA (Ref. 17) confirmed by a second value measured minimum 3 months later
 
◆ Clinical progression is defined as onset of obstructive symptoms requiring local treatment and demonstrated to be caused by cancer progression or evidence of metastases detected by clinical symptoms and confirmed by imaging
 
◆ Start of another line of systemic therapy in absence of progression
 
◆ Death due to any cause
 
 
Secondary endpoints:
 
 
◆ Clinical progression-free survival
 
◆ Time to next systemic anticancer therapy (including secondary hormonal manipulation)
 
◆ Proportion of patients switching from GnRH antagonists to GnRH agonists and total effective duration of treatment with the originally allocated drug.
 
◆ Overall survival
 
◆ Cancer specific survival
 
◆ PSA at six months after completion of RT
 
 
Safety will be scored by the CTCAE version 4.0. The major safety endpoints in this study are
 
 
◆ the incidence of clinical cardiovascular events – CCE (i.e. arterial embolic or thrombotic events, hemorrhagic or ischemic cerebrovascular conditions, myocardial infarction, and other ischemic heart disease) in patients who had cardiovascular events before entering the trial and in those without such events.
 
◆ Incidence of urinary tract infection
 

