	
 
◆ All secondary efficacy endpoints will be reported in the intent-to-treat population. A sensitivity analysis of the endpoint PSA at 6 months will also be conducted in the per protocol population
 
◆ Safety will be reported in the per protocol population 2 and in the safety population.
 
◆ Quality-of-life and other patient reported outcomes will be reported in the intent-to-treat population
 
◆ Testing strategy for the primary endpoint:  
The 2-sided 95% confidence interval for the hazard ratio for the treatment effect on the primary trial endpoint will be calculated based on a Cox regression model stratified for the stratification factors of the randomization.
 
The test for superiority is conducted first. If it does reject the null hypothesis of no difference (one-sided <math>P < 0.025</math>) then one concludes to superiority of the GnRH-antagonist.
 
If one does not, then the primary test for the non-inferiority question is conducted. If the upper bound of the 2-sided 95% confidence interval around the HR (agonist/antagonist) is <math>< 1.159</math> then one concludes to non-inferiority.
 
Otherwise, one concludes that neither non-inferiority nor superiority of the experimental treatment can be demonstrated compared to the standard treatment.
 
This strategy guarantees full control over the type I error rate of the trial.
 
 
◆ Analysis of secondary endpoints  
The secondary endpoint clinical progression-free survival is also assessed by means of cox regression stratified by the stratification factors of the randomization.
 
The secondary endpoints time to time to next systemic anticancer therapy (including secondary hormonal manipulation) and cancer specific survival are analyzed by means of a Fine-and-Gray model stratified by the stratification factors of the randomization.
 
Quality of life endpoints are analyzed by means of mixed effects regression models adjusted for the stratified by the stratification factors of the randomization. I-PSS scores over time will be reported as change scores from baseline. Health Economic analysis will be done using the scores from the EQ-5D-5L tool (Ref. 39)
 
The other secondary endpoints as well as the main safety endpoints are compared by means of logistic regression models stratified by the stratification factors of the randomization.
 
Other safety parameters are described as frequency tables.
 
 
◆ Interim monitoring
 
◆ No formal interim stopping rule based on efficacy is planned in this study. The central IDMC for the EORTC studies will review the trial at
 

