--	---

	
regular intervals (q2 years) to review the safety data of the study, and to monitor the assumptions driving the choice of the total number of patients needed to achieve the specified statistical power during the specified time frame; and to advise on an increase of the sample size if the event rate on the control group would appear lower than anticipated by design. The IDMC will also be asked to authorize any release of other data than efficacy during the course of the study, if such intention emerges. The first IDMC review will take place at year 2 or as soon as 10 Clinical Cardiovascular Events will have been recorded in the database

Translational research
	
This research project is optional.
 
All patients enrolled in the main study will be offered to participate in this translational research project. For the patients that will have consented, saliva will be collected and stored. Gene profiling of all samples will be performed in the future.
 
Saliva will be collected at the time of inclusion in the main study.

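### The on-study cardiovascular event list has no place for a cardiovascular or unexplained sudden death without a listed event, so such a death is scored as no event

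*Protocol*

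**What the plan says.** All places are in the Protocol summary.

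- **Objective(s).** A secondary objective is "documentation of effect of GnRH antagonists on clinically significant cardiovascular events in the subgroup of patients at high risk of such events at baseline".
- **Criteria for evaluation, Safety.** Two major safety endpoints are named. The first is "the incidence of clinical cardiovascular events", reported in men with and without such events before entry; the second is urinary tract infection. The cardiovascular term is spelled out after i.e. as "arterial embolic or thrombotic events, hemorrhagic or ischemic cerebrovascular conditions, myocardial infarction, and other ischemic heart disease".
- **Statistical methods, analysis of secondary endpoints.** "the main safety endpoints are compared by means of logistic regression models stratified by the stratification factors of the randomization". A competing-risk method is named only for time to next systemic therapy and for cancer specific survival: "cancer specific survival are analyzed by means of a Fine-and-Gray model stratified by the stratification factors of the randomization".
- **Criteria for evaluation, Efficacy.** Death enters the primary endpoint ("Death due to any cause"), overall survival and cancer specific survival.
- **Interim monitoring.** The first IDMC review falls at year 2 or "as soon as 10 Clinical Cardiovascular Events will have been recorded in the database".
- **Inclusion criteria.** Men on certain antiarrhythmic drugs need careful evaluation before either drug class is used, "because these drugs may prolong the QT-interval".

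**The concern.** The objective speaks of clinically significant cardiovascular events, but the endpoint that serves it is limited to thrombotic, cerebrovascular and ischaemic events. A cardiac death with none of these is clinically significant on any reading and still falls outside. Under a yes/no analysis with no stated handling of death, such a man is a non-event and can no longer become an event.

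The protocol acknowledges that both drug classes may affect the QT interval, so arrhythmic death is a harm it has in view. Men with a previous cardiovascular event, the group the objective is about, are where such deaths are most plausible.

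At stake is the cardiovascular comparison. If these deaths differ between arms, or are unaffected by treatment while listed events are reduced, the endpoint gives an incomplete picture. The trial is also open-label. Without a rule, whether an unexplained sudden death is placed under other ischaemic heart disease is left to someone who may know the arm.

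**Working it through.** **1. The plan's own figure.** The protocol states no rate, effect size or power for cardiovascular events. Its only design figure is for progression-free survival. The hazard ratio is ln(0.765)/ln(0.685) = 0.708. Schoenfeld's formula gives events = 4 × (1.960 + 0.842)² / (ln 0.708)² = 31.4 / 0.1192 = 263.3, rounded up to 264, as stated. Nothing in this point changes that number or the 885 patients.

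**2. How each type of death is scored under the text**

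| Outcome | Cardiovascular endpoint | Seen elsewhere |
|---|---|---|
| Fatal infarction, stroke, arterial thrombosis or other ischaemic event | Event | Progression-free and overall survival |
| Arrhythmic or heart failure death after an on-study listed event | Event (the earlier one) | As above |
| Arrhythmic or heart failure death, no listed event | No event | As above, plus adverse event tables if reported |
| Unexplained sudden death, no listed event | No event, unless judged ischaemic; no rule given | As above |

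Only the last two rows are affected.

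**3. Illustration of size.** Every rate here is an assumption. Suppose 30% of 885 men have a previous event: 885 × 0.30 / 2 = 133 per arm. Let p be the control-arm risk of a listed event (10% or 20%), halved in the experimental arm. Let q be the control-arm risk of cardiovascular death without a listed event (1%, 2% or 4%). Because q is defined as having no listed event, the two add without overlap.

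- Control-arm deaths missed = 133 × q
- Share of control-arm outcomes missed = q / (p + q)
- Risk ratio with these deaths included, treatment having no effect on them = (p/2 + q) / (p + q)
- Risk ratio with these deaths included, twice as frequent on the experimental arm = (p/2 + 2q) / (p + q)

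| p | q | Deaths missed (control) | Share missed | Ratio, no effect | Ratio, doubled |
|---|---|---|---|---|---|
| 10% | 1% | 1.3 | 9% | 0.55 | 0.64 |
| 10% | 2% | 2.7 | 17% | 0.58 | 0.75 |
| 10% | 4% | 5.3 | 29% | 0.64 | 0.93 |
| 20% | 1% | 1.3 | 5% | 0.52 | 0.57 |
| 20% | 2% | 2.7 | 9% | 0.55 | 0.64 |
| 20% | 4% | 5.3 | 17% | 0.58 | 0.75 |

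On the listed events alone the ratio is 0.50 in every row.

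**4. Does the death also suppress listed events?** A man who dies can have no later listed event. At p = 10%, the control-arm deaths above would have produced at most 1.3 × 10% = 0.1 to 5.3 × 10% = 0.5 further listed events. This is a fraction of an event, so the main effect is omission of the death itself.

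**5. IDMC trigger.** If the missed share held across the whole trial, ten listed events would correspond to 10 × (p + q)/p cardiovascular outcomes: 10 × 0.21/0.20 = 10.5 at the low end and 10 × 0.14/0.10 = 14 at the high end. The year-2 date limits any delay.

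**The case against.** Much of the case on the other side stands.

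- **Fatal listed events count.** A reader might infer that the endpoint leaves out cardiovascular death altogether. It does not: the list is not restricted to non-fatal events.
- **The deaths are recorded elsewhere.** All deaths enter progression-free and overall survival, toxicity is scored by CTCAE, and the IDMC reviews safety data every two years. An excess of fatal arrhythmia could be seen, though not in the endpoint built for the cardiovascular question.
- **Entry criteria lower the risk.** The exclusions cover QTc above 450 ms, other rhythm risk factors, QT-prolonging medication, NYHA class III or IV disease and ejection fraction below 50%. This makes the upper assumed death rates harder to defend. It does not remove the risk: NYHA class I or II disease and an infarction more than six months old are not excluded.
- **The list is a coherent construct.** The same term is a stratification factor, and a previous event cannot be a death. The objective is documentation, with no stated hypothesis or power. This supports keeping the list as a supporting version and leaving the stratification factor alone. It does not explain why an on-study cardiac death should be a non-event.
- **Other chapters may say more.** Only the summary is shown. Nothing in it widens the list, and i.e. closes it.

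**Conclusion.** The point holds in a limited form. A cardiovascular or unexplained sudden death without a listed event is scored as no event on one of two major safety endpoints, and it does not count toward the ten-event IDMC trigger.

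Two stronger readings are tempting, and the document does not support them. One is that the most serious cardiovascular outcome is treated as a success, or counted in the wrong direction. These men are counted as non-events, so information is omitted, and the true reversal is at most about half an event in the illustration. The other is that a particular number of events will be lost. The protocol gives neither the subgroup size nor any cardiovascular rate, so the 5% to 29% range, and the shift of a risk ratio from 0.50 to between 0.52 and 0.93, rest wholly on the assumed inputs.

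The severity is modest. The change is worth making because it is cheap and makes the cardiovascular comparison less open to distortion by death.

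**What to change.** 1. Define the on-study event as a listed event or death from a cardiovascular cause, including sudden death without another established cause. Use the same definition in men with and without a previous event, and for the IDMC count.
2. Report the present list as a supporting version for comparability.
3. Leave the baseline stratification factor as it is.
4. Make sure the cause-of-death record identifies cardiovascular and sudden deaths. Cancer specific survival by itself requires only that cancer deaths be told apart from others.
5. Fix the rule for classifying deaths in advance, because the trial is open-label.

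The cost is a short change to the endpoint definition, a derived variable, a written classification rule and possibly an extra field on the death form. The 264 events and 885 patients do not change. The downside is that some deaths will be classified with uncertainty; the supporting version shows how far the result depends on them.

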
Reference therapy, dose and mode of administration
	
Registered GnRH agonists, such as goserelin, triptorelin, leuprorelin, will be administered as 3 or 6 months depot formulation.
 
The minimum duration of androgen deprivation therapy with GnRH agonist or antagonist is 18 months.
 
For each patient, the duration of therapy must be elected upfront by the treating physician among three possible options: 18, 24 or 36 months. They shall also declare upfront the duration of the neoadjuvant treatment they intend to deliver to each patient (between 0 and 6 months).
 
A non-steroidal anti-androgen (e. g. flutamide, bicalutamide) will be given orally one week before the first injection of the GnRH agonist and will be continued for no longer than 8 weeks to protect against flare.

	
External beam radiotherapy to a dose of 78-80 Gy, delivered as one daily fraction, five days a week, started between d1 and month 6 of the androgen deprivation therapy as per institution policy. The irradiation is the same in both arms.
 
Day 1 (d1) of treatment in this study is the day of first injection of GnRH-agonist or GnRH-antagonist (depending on allocated treatment group) and corresponds to the start of treatment. Day 1 of treatment should start within 2 weeks after randomization.

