Statistical methods	
 
◆ Treatment allocation method: No blinding is applied in this study. Before the start of the hormonal therapy, the patients are allocated between the two treatment groups in a 1:1 ratio, by means of stratified blocked randomization with variable block sizes. Stratification factors will be the presence of previous clinical cardiovascular event (no vs yes), the country where the patient is treated, and the number of high risk factors that the patient presents (2 vs >2 high risk factors of relapse)
 
◆ Analysis populations 
 
◆ Intention-to-treat population: All randomized patients will be analyzed in the arm they were allocated by randomization.
 
◆ Per protocol population 1: All patients who are eligible and have received at least 6 months of the allocated treatment
 
◆ Safety population: All patients who have started their allocated treatment (at least one injection of the allocated treatment)
 
◆ Per protocol population 2 (adjusted for switch): All patients who are eligible and have started treatment censoring observations at the time of switching treatment (from GnRH-antagonist to GnRH-agonist) or stopping treatment in absence of progression.
 
 
 
 
Analysis methods:
 
 
◆ The primary analysis of the primary endpoint will be performed in the intent-to-treat population for the superiority test. Two sensitivity analyses will be conducted, repeating the test in the per protocol population 1 and in the per protocol population 2.
 
◆ If the superiority test fails to reject the null hypothesis of no difference a non-inferiority test will be conducted. To protect against the risk of false positive conclusions, the primary test for the non-inferiority question will be conducted in the in the per protocol population 2. The test in the intention-to-treat population and in the per-protocol population 1 will be performed as a first sensitivity analysis. A second sensitivity analysis will be conducted in intent-to-treat population.
 

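### The safety population is entered only by an injection of the allocated drug, so reference-arm men exposed only to the anti-androgen lead-in drop out of the planned safety analyses, with no matching loss in the antagonist arm

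*Protocol*

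**What the plan says.** All references are to the Protocol summary.

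- **Statistical methods, Analysis populations.** The safety population is "All patients who have started their allocated treatment (at least one injection of the allocated treatment". Per protocol population 2 is "All patients who are eligible and have started treatment censoring observations at the time of switching treatment (from GnRH-antagonist to GnRH-agonist", with censoring also when treatment is stopped without progression.
- **Statistical methods, analysis methods.** "Safety will be reported in the per protocol population 2 and in the safety population". No other set is named for safety.
- **Treatment, Reference therapy.** The non-steroidal anti-androgen is listed as part of the reference therapy and "will be given orally one week before the first injection of the GnRH agonist". Day 1 "is the day of first injection of GnRH-agonist or GnRH-antagonist (depending on allocated treatment group) and corresponds to the start of treatment".
- **Treatment, Test product.** The antagonist arm has no oral lead-in; its first protocol drug dose is the injection.
- **Criteria for evaluation, Safety.** The first major safety endpoint listed is "the incidence of clinical cardiovascular events", to be given for men with and without earlier cardiovascular events.
- **Statistical methods, Treatment allocation.** "No blinding is applied in this study", and "the patients are allocated between the two treatment groups in a 1:1 ratio" before hormonal therapy starts.

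**The concern.** A safety set should hold everyone exposed to a protocol drug. Here entry depends on an injection, while exposure in one arm starts a week before the injection. Exposed men can therefore be left out, and through the lead-in this can happen in one arm only.

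The exclusion can also depend on the outcome. A cardiovascular event or other toxicity during the lead-in week may be the reason why the injection is never given. The rule would then remove the man because of the very event that the analysis is meant to count.

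The second gap comes from the word allocated. A man who is given only the other GnRH drug has been treated, but he never has an injection of his allocated drug, so the wording leaves him out.

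The stake is modest but real. Cardiovascular events in men at high baseline risk are a secondary objective, and the main safety endpoints are to be compared between arms by stratified logistic regression. Where events are few, one omitted event is visible.

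**Working it through.** The plan gives no figure for this point. The check sets the definitions side by side and then shows the possible size as an assumption.

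**Step 1. Is the lead-in an exposure after randomization?** Yes. Allocation comes before hormonal therapy starts, the anti-androgen belongs to one arm only, and previous anti-androgen use is an exclusion criterion. Day 1 should fall within 2 weeks after randomization, which leaves room for the one-week lead-in.

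**Step 2. Who is in which set?** Per protocol population 2 is read here with the summary's own definition of the start of treatment, which is the first injection of the allocated group's drug.

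| Man | Safety population | Per protocol population 2 |
|---|---|---|
| Reference arm, anti-androgen only, never injected | Out: no injection | Out: treatment not started |
| Either arm, only the other GnRH drug injected | Out: no allocated injection | Out on this reading; open if the set is read without the Day 1 definition |
| Either arm, at least one allocated injection, later switch | In | In if eligible, censored at an antagonist-to-agonist switch |
| Antagonist arm, no injection | Out, but had no protocol GnRH drug or lead-in | Out |

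The first row is the firm gap, and nothing in the antagonist arm corresponds to it. The second row can occur in either arm.

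**Step 3. Possible size.**

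- Sample size: first-year accrual (76 + 124 + 174 + 227)/4 = 150.25, plus 2.45 years × 300 = 735, gives 885.25. This matches the stated 885.
- Reference arm at 1:1: 885/2 = 442.5.
- Assumed share with anti-androgen exposure only, 0.5% to 3%: 0.005 × 442.5 = 2.2 and 0.03 × 442.5 = 13.3, so about 2 to 13 men, all in the reference arm.
- The same assumed range for men given only the other drug, over both arms: 0.005 × 885 = 4.4 and 0.03 × 885 = 26.6, so about 4 to 27 men. The summary describes no route by which this would happen often, so the upper end is not a forecast.

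**Step 4. Effect of one omitted event.** With x events among 442 men, leaving out one man with an event changes the proportion from x/442 to (x − 1)/441. The drop is (442 − x)/(442 × 441), which is at most about 0.23 percentage points. It would be larger in the subgroup with earlier cardiovascular events, whose size is not given.

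**Step 5. Direction.** Losing men with lead-in events understates reference-arm toxicity. This limb therefore does not flatter the antagonist, but it under-reports harm and makes the comparison unequal.

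**The case against.** A reader might infer that these men vanish from all safety reporting. The documents do not support that. The data monitoring committee reviews the study's safety data and cardiovascular events recorded in the database, and neither is tied to an injection. Deaths enter the primary endpoint and overall survival in the intention-to-treat population, and quality of life and other patient-reported outcomes are analysed there too. The gap lies in the planned safety analyses only.

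A reader might also infer that all toxicity in the lead-in week is lost. No text shown says that adverse events are counted only from Day 1. Men who take the lead-in and are then injected are in the safety population, and nothing excludes their earlier events. The loss is confined to men who stop before the injection.

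A third tempting reading is that men who cross over are dropped. The crossover that the summary foresees is from antagonist to agonist during treatment, and such a man stays in the safety population after one allocated injection. Only a man who never receives his allocated drug is affected. Even for him, per protocol population 2 says started treatment without the word allocated, so an eligible agonist-arm man given the antagonist could be counted there if that definition is read alone. That is an ambiguity and not a safeguard.

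It is also fair to say that no rate is documented, that a few men lost in one week are unlikely to move endpoints collected under 18 to 36 months of therapy, and that grouping by drug received or by allocation is partly a matter of convention. These points limit the size of the problem. They do not answer the one-sided exclusion of exposed men.

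**Conclusion.** The point holds in a narrow form. As worded, the safety population leaves out reference-arm men exposed only to the anti-androgen, and per protocol population 2 leaves them out as well once the summary's definition of the start of treatment is applied. The loss is in one arm only and may be caused by the event being measured. Men who receive only the non-allocated GnRH drug are also outside the safety population, which is the weaker part of the point because it needs a man who never gets his allocated drug.

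The number affected is not documented and is probably small; the 2 to 13 men above rest on an assumed 0.5% to 3%. No bias of a given size in any safety estimate is shown. Efficacy results, the sample size and the type I error rate do not depend on this definition. This is an inexpensive improvement and not a threat to the trial's conclusions.

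**What to change.** Replace the definition with one that follows exposure, for example: the safety population comprises all randomized men who received at least one dose of any protocol drug (anti-androgen, GnRH agonist or GnRH antagonist). Men who received only the anti-androgen stay in the reference arm. Men who received only the GnRH drug they were not allocated are grouped by the drug received. Adverse events from the first dose of any protocol drug are included.

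The last sentence makes explicit something on which the summary is silent; it does not correct a stated rule. Per protocol population 2 can stay as it is.

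The cost is a short change of wording in the protocol or the statistical analysis plan. It needs no new data, provided that events in the lead-in week are recorded, and the summary does not state the collection window. The drawback is that a few men may be analysed for safety outside their allocated arm. A footnote with their number in each arm would make this visible.
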